## **4 SUBJECT SELECTION**

### **4.1 Inclusion Criteria**

Subjects must meet all of the following criteria to be included in the study:

1. Signed informed consent.
2.  $\geq 5$  years of age:
  - a) adult cohorts 1 through 3:  $\geq 18$  years of age;
  - b) pediatric cohorts 4 and 5: 12 to 17 years of age; and
  - c) pediatric cohorts 6 and 7: 5 to 11 years of age.
3. Clinical diagnosis of MPS I; IDUA deficiency confirmed by gene sequencing.
4. Sexually mature subjects must agree to use a barrier contraceptive method for prevention of AAV transfer as follows: for female subjects this means that the subjects' partners must use a condom from dosing with SB-318 until at least 3 consecutive plasma samples after administration of SB-318 are negative for AAV2/6; for male subjects this means that the subjects must use a condom and must refrain from sperm donation from the time of SB-318 until at least 3 consecutive semen samples after administration of SB-318 are negative for AAV2/6. Additionally, female participants of child-bearing potential must consent to use a highly effective method of contraception.
5. Magnetic resonance imaging (MRI) negative for liver mass as read by a radiologist.

### **4.2 Exclusion Criteria**

Subjects who meet any of the following criteria will be excluded from participating in the study:

1. Known to be unresponsive to ERT.
2. Neutralizing antibodies in serum (immune response) to AAV2/6.
3. Serious intercurrent illness or clinically significant organic disease (unless secondary to MPS I) such as cardiovascular, hepatic, pulmonary, neurologic, or renal disease.
4. Receiving antiviral therapy for hepatitis B or C, or with active hepatitis B (HBV DNA positive or HBV surface antigen positive) or hepatitis C (HCV RNA viral load) or human immunodeficiency virus (HIV)-1/2 (HIV RNA viral load or HIV antibody positive); to be considered negative for hepatitis C after treatment of an active HCV infection, viral assays in 2 samples collected at least 6 months apart must be negative.
5. Lack of tolerance to ERT with significant infusion-associated reactions (IARs) or occurrence of anaphylaxis.
6. Polymorphisms in the ZFN-targeted region of the albumin locus.
7. Liver fibrosis score of 3 or 4 on a 0 to 4 point scale ([Desmet et al. 1994](#)) if subject has had a liver biopsy within 2 years of Screening.
8. Markers of hepatic dysfunction as evidenced by one or more of the following:
  - a. Platelet count  $<100,000/\mu\text{L}$

- b. Albumin  $\leq 3.2$  g/dL
- c. Total bilirubin  $> 1.5 \times$  upper limit of normal (ULN) and direct bilirubin  $\geq 0.5$  mg/dL
- d. Alkaline phosphatase  $> 2.0 \times$  ULN
- e. ALT or AST  $> 2.0 \times$  ULN

9. Creatinine  $\geq 1.5$  mg/dL.
10. Weight  $< 20$  kg at Screening.
11. Pregnant or breastfeeding female.
12. Contraindication to the use of corticosteroids.
13. Current treatment with systemic (IV or oral) immunomodulatory agent or steroid use (topical treatment allowed, e.g., for asthma or eczema).
14. History of active malignancy in past 5 years (non-melanoma skin cancer or cervical cancer *in situ* permitted).
15. Participation in prior investigational drug or medical device study within the previous 3 months.
16. Prior treatment with a gene therapy product.
17. History of alcohol or substance abuse that in the opinion of the Principal Investigator may interfere with study compliance.
18. History of therapeutic non-adherence.
19. Elevated or abnormal circulating  $\alpha$ -fetoprotein (AFP).
20. Any other reason that, in the opinion of the Principal Investigator or Medical Monitor, would render the subject unsuitable for participation in the study.

## **5 INFORMED CONSENT**

Informed consent must be obtained from the adult subjects or parents or guardians and assent must be obtained from pediatric subjects as institutional policy allows before any study-related screening activity is undertaken that is not part of routine care. Informed consent may be obtained separately for Screening blood tests only (to determine eligibility based on neutralizing antibodies to AAV 2/6 and single-nucleotide polymorphism [SNP] analysis) prior to obtaining full study Informed Consent, if allowed by the local institutional review board (IRB) or institutional ethics committee (IEC) or equivalent. The subject's legally authorized representative may also provide informed consent for subject participation if allowed by the local IRB/IEC or equivalent.

The Principal Investigator or designated personnel will explain to each subject or the subject's legally authorized representative the nature of the study, its purpose, the procedures, the expected duration, alternative therapies available, and the benefits and risks of participation. The subject or the subject's legally authorized representative will receive an information and consent document, with the opportunity to ask questions, and will be informed that participation is voluntary, and that the subject can withdraw from the study at any time without any impact on the subject's future clinical care. The subject or the subject's legally authorized representative will receive a copy of the signed and dated written informed consent form. Each subject will be re-consented at the time of any informed consent amendment, as applicable, and will be provided a copy of the signed and dated revised consent form.

## **6 STUDY METHODOLOGY**

Prior to initiation of this study, the study site shall be approved by the IRB/IEC or equivalent. Subjects must be willing to participate in all study procedures related to this protocol.

The following sections describe all study procedures. Additional detailed instructions will be provided in the Study Reference Manual, Laboratory Manual, and Pharmacy Manual. A table of all study procedures is presented in the Schedule of Events (see [Appendix 1](#)).

### **6.1 Screening**

The objective of Screening is to identify subjects who meet the stated inclusion and exclusion criteria and who are willing and able to participate in the study. Screening may take up to approximately 3 months and may be performed across several visits.

The following assessments and procedures will be performed:

- Obtain a signed and dated subject informed consent form and authorization document to use and disclose medical information prior to performing any study-specific procedures.
- Obtain a complete medical history.
- Review and record concomitant medications.
- Review the inclusion and exclusion criteria.
- Collect demographic information.
- Assign a subject number.
- Physical examination.
- Vital signs.
- Assessment of AEs.
- ERT administration log.
- 12-lead electrocardiogram (ECG).
- Echocardiogram (ECHO).
- Chest x-ray.
- Pregnancy test (for females of childbearing potential only).
- Clinical laboratory tests.
- Liver panel.
- MPS I gene sequencing.
- SNP analysis.
- Viral load.
- Neutralizing antibodies to AAV2/6.

- GAG testing in urine (collect samples on 3 separate days, each collection occurring at least 7 days after the previous, and all collections occurring at least 7 days after ERT administration [+/-1 day] but prior to the next ERT infusion).
- IDUA / GAG testing in blood (collect 7 days after ERT administration [+/-1 day]).
- Circulating AFP level.
- Pulmonary function tests (PFTs).
- VABS-II (Vineland Adaptive Behavior Scales) test.
- Neurocognitive abilities assessment.
- MRI of liver.

Subjects may be re-screened for participation in the study in the judgement of the Principal Investigator and after consultation with Sangamo. For re-screening, the following assessments performed in the previous 6 months may be used for evaluation of inclusion/exclusion criteria at the judgement of the Principal Investigator:

- ECHO.
- Chest X-Ray.
- PFTs.
- MRI of liver and/or brain and cervical spine.

Further, genetic marker analysis including SNP analysis and MPS I sequencing will not be repeated as results of these assessments do not change over time.

## 6.2 Subject Enrollment

Before a subject is assigned to a dose cohort, the study site personnel must verify that the subject fulfills all eligibility criteria.

The pediatric cohorts will be enrolled only after review of cumulative adult safety data by an independent, external SMC (see [Section 12.3](#)).

## 6.3 Baseline

Baseline assessments will be performed within 21 days prior to SB-318 infusion.

In subjects receiving ERT, ERT shall be withheld during the week of the administration of SB-318 to enable accurate baseline testing

The following assessments and procedures will be performed:

- Review and record concomitant medications.
- Physical examination.
- Vital signs.
- Assessment of AEs.
- ERT administration log.
- Joint range of motion (JROM).

- Neurologic cranial nerve exam and muscle strength testing of the upper extremities.
- 12-lead ECG.
- Pregnancy test (for females of childbearing potential only).
- Clinical laboratory tests.
- Liver panel.
- Chimerism assay (for post-HSCT subjects only).
- GAG testing in urine.
- IDUA / GAG testing in blood.
- Vector genome PCR in plasma, saliva, urine, stool, and semen (males only).
- PFTs.
- 6-minute walk test (6MWT).
- Visual acuity test and corneal clouding exam.
- Neurocognitive abilities tests by WASI-II (Wechsler Abbreviated Scale of Intelligence), WPPSI-IV (Wechsler Preschool and Primary Scale of Intelligence), or BSID-III (Bayley Scales of Infant Development), and by VABS-II.
- MRI of brain and cervical spine.
- Adrenocorticotrophic hormone (ACTH) stimulation (cosyntropin) test (prior to prednisone or equivalent corticosteroid).
- Liver biopsy.
- Lumbar puncture.
- Immunogenicity assays.
- Prednisone or equivalent corticosteroid administration (starting 2 days before SB-318 infusion).

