## 8.2 Prednisone (or Equivalent Corticosteroid)

Prednisone is a glucocorticoid. Glucocorticoids are adrenocortical steroids, both naturally occurring and synthetic, which are readily absorbed from the gastrointestinal tract.

The following adverse reactions (ARs) have been associated with the use of glucocorticoids:

- Thinning of bones (osteoporosis), which may lead to fractures or compressions, especially true of vertebral bodies (backbone).
- Loss of blood supply to bones (aseptic necrosis), which may cause severe bone pain, fractures (especially of the hip and shoulder), and which may require surgical correction.
- High blood pressure (hypertension).
- Increased pressure in the eye (glaucoma).
- Permanent clouding of vision in one or both eyes (cataracts).
- Weight gain with increased appetite and fluid retention.

- Facial fullness.
- Increase in body hair and acne, and tendency to easy bruising and thinning of the skin.
- Increased risk of infections while on high dose continuous steroid therapy.
- Interference with growth.
- Muscle cramps and joint pain.
- Changes in the menstrual cycle.
- Elevations in blood sugar (diabetes).
- Suppression of adrenal glands' ability to make necessary cortisone at times of stress (adrenal insufficiency).
- Irritation of stomach and esophagus with possible ulcer type symptoms and, rarely, bleeding.
- Emotional disturbances.

Dietary guidelines will be provided to subjects while on prednisone or equivalent corticosteroid to help alleviate some of the side effects including blood sugar elevation, associated with the use of glucocorticoids (refer to the Study Reference Manual).

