## APPENDIX 3: IMMUNOSUPPRESSION REGIMEN

Weight of Subject (kg)	Oral Prednisone (mg/day)					
	Day -2 to Day 0	Week 1	Week 2	Week 3-16	Week 17-19	Week 20
≥ 60	60	60	30	15	5	STOP
55	60	60	30	15	5	STOP
50	50	50	25	15	5	STOP
45	45	45	25	15	5	STOP
40	40	40	20	10	5	STOP
35	35	35	20	10	5	STOP
30	30	30	15	10	5	STOP
<30	1 mg/kg	1 mg/kg	0.5 mg/kg	0.25 mg/kg	0.25 mg/kg every other day	STOP

Prednisone or equivalent corticosteroid regimen is commenced 2 days prior to Day 0 of SB-318 infusion and given once daily unless otherwise stated. Subject's liver function will be monitored twice a week while on prednisone or equivalent corticosteroid. Blood for liver panel shall be drawn 2 to 4 days apart when possible, except for the first week when it will be drawn on the Day 1 and Day 7 visits. Tapering of prednisone or equivalent corticosteroid will only proceed if ALT/AST activity levels are stable or declining (based on the 2 assessments of the preceding week).

If subjects develop increased ALT > 2 fold Baseline while on prednisone or equivalent corticosteroid or after stopping prednisone or equivalent corticosteroid, the prednisone or equivalent corticosteroid regimen may be adjusted or restarted at the Principal Investigator's discretion after consultation with the Medical Monitor.

Twice a week liver panel testing should continue until the prednisone or equivalent corticosteroid course has been terminated.

An ACTH stimulation (cosyntropin) test will be performed prior to the first prednisone or equivalent corticosteroid dose and again during Week 20 or at the end of the scheduled taper to ensure that the adrenal cortical function has not been suppressed. Should prednisone or equivalent corticosteroid treatment be repeated due to increased transaminase activity, the ACTH stimulation test will be repeated at the end of taper at the Principal Investigator's discretion.

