3.4. Dose Modifications

No dose modifications are possible within an individual subject since this is a single infusion study.

4. General Statistical Considerations

Study days will be numbered relative to the date of SB-318 infusion. For assessments on or after the date of SB-318 infusion, the study day of events from SB-318 infusion is calculated as the date of event minus the date of infusion. For assessments prior to the date of SB-318 infusion, the study day of events from SB-318 infusion is calculated as the date of event minus the date of infusion. Thus, the study day of event before the date of the infusion will be negative number, and the study day of the date of infusion will be 0.

Baseline is defined as the last non-missing measurement prior to the SB-318 infusion. Where only date is available, the date of the collection must be prior to the date of SB-318 infusion. Where time is also available, the time of the collection must be prior to the time

of SB-318 infusion. For example, for vital signs parameters, measures that are taken at the latest time prior to the infusion will be defined as baseline values. Measurements that are obtained after infusion will be considered as post-baseline values. If the measurement of a variable is not made on a given subject prior to infusion, then that subject will be considered not to have a baseline value for that variable. Change from baseline is defined as post-baseline assessment minus baseline assessment.

Continuous data will be summarized using the following descriptive statistics: number of subjects (n), mean, standard deviation (SD), median, minimum and maximum, where appropriate. Categorical data will be summarized using the frequency count (n) and percentage (%) of subjects for each category, where appropriate.

Unless specified otherwise, all the summary tables will be presented by treatment cohort and overall, and all the collected data will be presented in the listings, and data displayed in the listings will be sorted by treatment cohort and subject identifier.

No imputation will be applied for missing data unless otherwise specified.

All analyses will be conducted using SAS® Version 9.3 or later. The Medical Dictionary for Regulatory Activities (MedDRA 23.0) will be used for coding adverse events.

Concomitant medication data will be coded using the World Health Organization (WHO) Drug Dictionary.

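### Baseline blood pressure and heart rate are read after prednisone has started, and baseline labs may be, so change-from-baseline tables can understate an early steroid effect

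*Protocol*

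**What the plan says.** Appendix 3 of the protocol fixes the start of the steroid course: "Prednisone or equivalent corticosteroid regimen is commenced 2 days prior to Day 0 of SB-318 infusion and given once daily unless otherwise stated". The course opens at its highest daily level and tapers to a scheduled stop at Week 20. Section 6.3 lists the same start among the Baseline items, "Prednisone or equivalent corticosteroid administration (starting 2 days before SB-318 infusion", and allows Baseline assessments at any time in the 21 days before infusion. Only one of them is ordered relative to the steroid, the ACTH test: "stimulation (cosyntropin) test (prior to prednisone or equivalent corticosteroid". Clinical laboratory tests, the liver panel and Baseline-visit vital signs carry no such condition.

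Sections 7.1.2 and 7.1.3 require temperature, heart rate, respiratory rate and blood pressure before, during and after the infusion. Section 6.4 schedules no clinical laboratory tests on Day 0.

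SAP Section 4 states the general rule, "Baseline is defined as the last non-missing measurement prior to the SB-318 infusion", and uses vital signs as its example: "measures that are taken at the latest time prior to the infusion will be defined as baseline values". A value with a date but no clock time must come from a day before the infusion. Neither rule mentions the steroid. Protocol Section 8.2 names hypertension, weight gain and "Elevations in blood sugar (diabetes" among the reactions to glucocorticoids.

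**The concern.** A change-from-baseline table for safety is normally read as change from the untreated state. For blood pressure and heart rate this plan gives change from a state in which the steroid has already been started. For chemistry and hematology the reference can differ between subjects: one may be drawn three weeks before infusion and off steroid, another on the day before infusion and on it. With one or two subjects planned per cohort, one such difference can alter a cohort's row.

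The shift tables have the same weakness. A glucose value already High on the day before infusion is displayed as High to High, with no worsening. AE recording can be affected too. Protocol Section 10.1.1 counts a finding as an AE when it worsens relative to Baseline, and Section 10.3 requires Grade 3 and 4 laboratory results to be reported when they are more severe than at Baseline. A Baseline-visit draw taken after the first dose therefore moves the yardstick for some reported events.

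**Working it through.** The plan states no figure for this point and tests no hypothesis (SAP Section 1), so there is nothing to reproduce. The check is one of ordering, plus arithmetic on Appendix 3.

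1. **Vital signs.** Prednisone is due on Day -2 and Day -1, and a third dose on Day 0 may precede the infusion. The pre-infusion reading is compulsory on Day 0, and Listing 16.2.8.2 carries date and time. The latest pre-infusion blood pressure and heart rate therefore follow two or three doses whenever the protocol is followed.

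2. **Weight.** Section 9.5 counts weight as a vital sign, so it is due on Day 0. It is not among the four signs required before infusion. A date-only Day 0 weight cannot be baseline, and the programming note to Table 14.3.5 lists Day 0 as a post-baseline visit and gives Day 0 weight a single row. Only a timed, pre-infusion Day 0 weight would be an on-steroid baseline by design. Otherwise baseline weight is the Baseline-visit value, which may precede prednisone.

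3. **Exposure before and after baseline** (Appendix 3, 55 kg and above): 3×60 + 7×60 + 7×30 + 98×15 + 21×5 = 2385 mg over 3 + 7 + 7 + 98 + 21 = 136 days. Before infusion: 2×60 = 120 mg, or 120/2385 = 5.0%; 3×60 = 180 mg, or 180/2385 = 7.5%. The lowest shares are in the 30 kg row: 60/1490 = 4.0% and 90/1490 = 6.0%. Across all rows the range is 4.0% to 5.0% for two doses and 6.0% to 7.5% for three, so at least 92% of the scheduled dose follows baseline.

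4. **Chance that Baseline labs are on steroid.** The documents give no draw dates, so these are assumptions.
   - Draw day uniform over 21 days: 1/21 = 4.8% if only Day -1 follows a dose; 2/21 = 9.5% if Day -2 does too.
   - Draws clustered in the last seven days: 2/7 = 28.6%, or 3/8 = 37.5% if a pre-infusion Day 0 draw is counted. Section 6.3 withholds ERT in the infusion week for the sake of baseline testing, which makes some late sampling plausible.

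5. **Effect on the tables.** Let U be the untreated level, e0 the steroid effect present at baseline and et the effect at visit t. The table shows (U + et) − (U + e0) = et − e0, whereas change from the untreated state is et. While the steroid acts, the rise is understated by e0. Once it has worn off, et = 0 and the table shows −e0. The documents give no value for e0. On an assumed range of 0 to 10 mmHg systolic, the distortion is 0 to 10 mmHg: nothing at the lower end, and at the upper end a sustained 10 mmHg rise displayed as no change.

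6. **Visits concerned.** Sections 6.5 to 6.9 schedule 20 vital-sign visits after Day 0. Eight (Day 1, Day 7, Weeks 2, 4, 6, 8, 12 and 16) fall within the course. Twelve (Weeks 20, 24, 36 and 48, and eight from Month 15 to Month 36) fall at or after its nominal end. The split is only nominal: Section 6.8 lists prednisone through Week 20 while Appendix 3 shows it stopped in Week 20, which must be reconciled. The taper also depends on ALT/AST, and the course can be restarted.

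**The case against.** The strongest reply is that an infusion-anchored baseline is a legitimate choice. The objective is the safety of SB-318, defined as three vectors; prednisone is recorded as a concomitant medication; and treatment-emergent events are also counted from infusion. A pre-prednisone baseline would put steroid effects into columns headed SB-318. That argument stands against replacing the main definition, but not against a second reference.

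It is also true that little is lost from view. Table 14.3.5 prints actual values beside changes, all laboratory values are listed with abnormal flags, all AEs are listed, and with so few subjects a reader can compare Screening with later values by hand. This limits the harm, but the change and shift tables would still carry an unstated and possibly mixed reference. Events starting on Day -2 or Day -1 are listed but are not treatment-emergent.

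The laboratory point is conditional on a late draw, and glucose is the only laboratory measure named in Section 8.2. The case for hematology or the liver panel is weaker and rests on consistency.

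A reader might infer that baseline weight is always on steroid, or that the tables hide the named harms. The documents support neither. The timing of Day 0 weight is unsettled, and at least 92% of the scheduled dose comes after baseline, so a slow effect such as weight gain remains mostly visible. Nor can one conclude that every subject's figures are biased: Section 8.2 gives neither onset time nor size, and e0 may be zero.

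**Conclusion.** The point holds in a limited form. With the protocol followed, baseline blood pressure and heart rate are on-steroid readings in every subject; this follows from the ordering alone. Baseline glucose and other labs are on steroid in some subjects only if drawn after the first dose, which nothing prevents. The displays can therefore understate an early rise in blood pressure or glucose and can show an apparent fall after the taper. The amount cannot be computed from the documents. The 0 to 10 mmHg range and the 4.8% to 37.5% range for lab draws rest on the stated assumptions. For weight the documents are unclear and need a decision. The definition of the primary endpoint, incidence of treatment-emergent AEs, is not in question, although AE recording refers to Baseline. This is a worthwhile, inexpensive improvement to reporting; it does not invalidate the safety analysis.

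**What to change.** Keep the last pre-infusion value as the main baseline in SAP Section 4. Then:

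- Prespecify a second reference: the last non-missing value before the first prednisone dose, from the Baseline visit or, failing that, Screening. Show change from it in Table 14.3.5 and in the chemistry and hematology change and shift tables (14.3.4.1, 14.3.4.2, 14.3.4.4 and 14.3.4.5). Screening values should be steroid-free, because exclusion criterion 13 bars current systemic steroid use.
- Flag every baseline taken after the first prednisone dose, which requires dose and draw times to be available.
- State whether Day 0 weight is baseline or post-baseline.
- For subjects not yet dosed, extend the qualifier that Section 6.3 attaches to the ACTH test to Baseline clinical laboratory tests and Baseline-visit vital signs. If the liver panel is included, reconcile this with Appendix 3, which uses a multiple of Baseline ALT as a reference.

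The cost is SAP wording and one extra display, with no new visit or sample. The Section 6.3 change is a protocol amendment needing IRB/IEC approval, and is of use only if dosing is still to come; the shells are dated January 2022. Where only a Screening value precedes prednisone, the second reference can be up to about 3 months older than the Baseline visit, so its date should be shown.
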